7.7.7.2 Assessment period

Adverse events occurring between obtaining the legal representative's informed consent (for new subjects) or initiation of study drug administration in this study (for consecutive subjects) and 7 days after the final administration of study drug (the follow-up period) as well as adverse events consecutive from the preceding study at the initiation of study drug administration in this study (only if applicable) will be assessed. For consecutive subjects, adverse events that occurred between obtaining informed consent for this study and initiation of study drug administration in this study will be assessed in the preceding study. In the case of withdrawn subjects, the principal investigator or sub-investigator will assess adverse events up to 7 days after final administration of the study drug. Appropriate follow-up will be continued until one of the following, and the outcome will be determined on that basis: (i) the relevant adverse event recovers to the pre-administration state (if consecutive from the preceding study, it should be recovered to the pre-administration of the preceding study); (ii) the subject's condition stabilizes or becomes chronic; (iii) the subject is lost to follow-up; or (iv) the principal investigator or sub-investigator judges further assessment to be unnecessary. In addition, if the subject stops visiting hospital during the study, he/she will be followed up by an appropriate method such as by telephone, and the findings will be entered in the CRF.

If the above adverse event follow-up has to be continued for 28 days or more after completion of administration, the outcome at the earliest date after 28 days after completion of administration will be recorded in the CRF.

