7.7.7.11 Adverse events during study drug administration

Adverse events with onset after the initial study drug administration are taken to be treatment-emergent adverse events (TEAE). For consecutive subjects, of adverse events consecutive from the preceding study at initiation of study drug administration in this study, adverse events that started after initiation of study drug administration in the preceding study are also taken to be TEAEs of this study.

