8.11.1 Adverse events

Adverse events will be classified by system organ class and preferred term, in accordance with MedDRA. Of the adverse events reported using CRFs, TEAEs will be used for safety analysis. TEAEs are defined in Section 7.7.7.11 .

The number of subjects suffering TEAEs, and the numbers suffering death, other serious TEAEs, TEAEs leading to discontinuation of administration, and TEAEs leading to dose reduction will be determined. The TEAE rate and 95% confidence interval will be calculated by the Clopper-Pearson method. The number

of adverse events will also be included. Adverse drug reactions will be summarized in the same manner as TEAEs. Adverse drug reactions are defined in Section 7.7.7.4 .

As summarization of TEAEs by system organ class and preferred term, the number and proportion of subjects suffering these events will be shown. In addition, TEAEs will be summarized by severity, onset timing, and outcome. Adverse drug reactions will be summarized similarly.

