10.1 Adverse events and adverse drug reactions

Adverse events occurring at or after the initiation of the open-label extension study and continuing from the preceding study will be evaluated. Reported adverse events will be converted to Medical Dictionary for Regulatory Activities (MedDRA) terms, and tabulated by system organ class and preferred term.

- 1) The number of subjects with a given adverse event and the number of cases will be determined, and the incidence rate and 95% confidence interval will be calculated. The incidence rate will be obtained as the proportion of subjects in the analysis set with a specific adverse event, and the confidence interval for the incidence rate will be determined by the Clopper-Pearson method. Totaling will be performed in a similar manner to above with deaths, other serious adverse events, adverse events leading to administration discontinuation, adverse events leading to dose reduction, adverse drug reactions, deaths as adverse drug reactions, other serious adverse drug reactions, adverse drug reactions leading to administration discontinuation, and adverse drug reactions leading to dose reduction. The relevant definitions are shown below.

Death	Adverse event with “Death” as the outcome
Other serious adverse event	Adverse event in the seriousness category “Serious”, except for death
Adverse event leading to administration discontinuation	Adverse event for which the study drug action is “Administration discontinuation”
Adverse event leading to dose reduction	Adverse event for which the study drug action is “Dose reduction”
Adverse drug reaction	Adverse event with the causal relationship with the study drug judged to be other than “Not related”
Death as adverse drug reaction	Death, with the causal relationship with the study drug judged to be other than “Not related”
Other serious adverse drug reaction	Other serious adverse event with the causal relationship with the study drug judged to be other than “Not related”
Adverse drug reaction leading to administration discontinuation	Adverse event leading to administration discontinuation, with the causal relationship with the study drug judged to be other than “Not related”
Adverse drug reaction leading to dose reduction	Adverse event leading to dose reduction, with the causal relationship with the study drug judged to be other than “Not related”

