- 2) The number of subjects with a given adverse event, the number of cases, and the incidence rate will be determined by adverse event system organ class and preferred term. However, when calculating the number of subjects with a given adverse event and the incidence rate, if the same adverse event occurs more than once with the same subject, these events will be taken to be have affected one subject. Adverse drug reactions will be tabulated similarly.
- 3) With respect to adverse events with an incidence of 2% or more, the number of subjects, number of cases, and incidence rate will be calculated for each adverse event preferred term. Adverse drug reactions will be tabulated similarly.
- 4) The number of subjects and incidence rate will be calculated for each severity and outcome category, by adverse event system organ class and preferred term. If the same adverse event occurs more than once in different categories with the same subject, it will be taken to have occurred once, in the category with the highest of the below priority ranks. Adverse drug reactions will be tabulated similarly.

Priority rank	Survey item category	
	Severity	Outcome
1	Severe	Death
2	Moderate	Recovery with sequelae
3	Mild	No improvement
4		Partial recovery
5		Recovery
6		Unknown

- 5) The number of subjects and the incidence rate will be calculated for each onset timing category (weeks 0 to 8; weeks 8 to 16, weeks 16 to 24, weeks 24 to 32; weeks 32 to 40; weeks 40 to 48; weeks 48 to 50; later than week 50) for adverse events during the treatment period, by system organ class and preferred term. The denominator of the incidence rate will be the number of subjects with administration duration no shorter than the lower limit of each onset time category. The onset timing will be calculated as follows:

Onset timing [day]

$$= (\text{onset date}) - (\text{administration initiation date in the open-label extension study}) + 1$$

When calculating the number of subjects and the incidence rate, if the same adverse event occurs in different categories more than once in the same subject, it will be taken to have occurred with one subject in each of the relevant categories. Adverse drug reactions will be tabulated similarly.

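### SAP 10.1 omits the protocol's treatment-emergent condition, so carried-over events that began before any study drug count in the main safety incidences

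*SAP*

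**What the plan says.** Protocol 8.11.1 fixes the scope of the safety analysis: "Of the adverse events reported using CRFs, TEAEs will be used for safety analysis". It refers to protocol 7.7.7.11 for the definition, which has two parts. The general rule is "Adverse events with onset after the initial study drug administration are taken to be treatment-emergent adverse events (TEAE"). For consecutive subjects it adds a conditional rule for events still ongoing when dosing starts here: "adverse events that started after initiation of study drug administration in the preceding study are also taken to be TEAEs of this study".

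Collection is wider than analysis. Under protocol 7.7.7.2 new subjects' events are recorded from consent. For consecutive subjects, "adverse events consecutive from the preceding study at the initiation of study drug administration in this study (only if applicable) will be assessed", with no limit on when those events began.

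SAP 10.1 opens with its own scope: "Adverse events occurring at or after the initiation of the open-label extension study and continuing from the preceding study will be evaluated". No event can both start in this study and continue from the last one, so the sentence must mean the two groups together. The tables in items 1 to 4 and 7 rest on it. The SAP text available for this review does not use or abbreviate the term treatment-emergent in the body or in the abbreviation list, and does not cite protocol 7.7.7.11. Some opening pages of the SAP were not available.

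**The concern.** Because the CRF holds more than the protocol intends to analyse, the TEAE rule is the only step that removes events which predate study drug. SAP 10.1 does not contain that step. A programmer working from the SAP would keep every event flagged as continuing from the preceding study, including any that began before the subject's first dose there.

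Long-term safety is the primary objective, and the item 1 incidences with their 95% intervals are its main output. Two analysts, one following the protocol and one following the SAP, could report different numbers from the same data. Protocol 8.1 requires the SAP to give the reason for any change to the planned analysis; the available text gives none.

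**Working it through.** **1. Scope, side by side**

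| Event | Protocol 7.7.7.11 / 8.11.1 | SAP 10.1 as written |
|---|---|---|
| Onset after first dose in this study | counted | counted |
| Carried over, began after first dose in preceding study | counted | counted |
| Carried over, began before first dose in preceding study | not counted | counted |
| New subject, onset on registration day | not counted | counted if initiation means Visit 2; not if it means first dose |

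The third row does not depend on how *initiation* is read. The fourth does, and the available SAP text does not define the word. Protocol 8.10 and 8.11.2 equate initiation of this study with Visit 2. Protocol 5.2 starts dosing the day after Visit 2, so on that reading the extra window is one day.

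**2. Denominator**

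The documents give no event counts, so the registration target stands in for the safety-analysis set. Checking that target: 100 / (1 − 0.25) = 133.3, rounded up to 134, against 135 stated; 135 × 0.75 = 101.25 completers. The figure reproduces within one subject.

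**3. Effect of one misclassified subject**

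SAP 10.1 defines incidence as subjects with the event divided by subjects in the analysis set. One extra subject adds 1/135 = 0.74 percentage points to a line, or nothing if that subject already counts in that line.

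The Clopper-Pearson limits for k of n are the 0.025 quantile of Beta(k, n − k + 1) and the 0.975 quantile of Beta(k + 1, n − k). With n = 135 and assumed counts:

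| TEAE subjects | Incidence (95% CI) | With one pre-drug event counted |
|---|---|---|
| 0 | 0.0% (0 to 2.70) | 0.7% (0.02 to 4.06) |
| 2 | 1.5% (0.18 to 5.25) | 2.2% (0.46 to 6.36) |
| 68 | 50.4% (41.64 to 59.08) | 51.1% (42.37 to 59.81) |

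Item 3 tabulates terms with an incidence of 2% or more. Since 0.02 × 135 = 2.7, three subjects are needed, so one misclassified subject can move a term from two to three and into that table. Rare terms are the most exposed; the overall incidence hardly moves.

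**4. Onset timing in item 5**

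Item 5 computes onset date minus the "administration initiation date in the open-label extension study", plus 1. An onset 7 days before that dose gives −7 + 1 = −6; the day before gives −1 + 1 = 0. No onset category covers such values. This applies to every carried-over event, including those the protocol counts as TEAEs.

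**The case against.** The best defence is that the SAP is a loose rendering of the protocol's rule. Its introduction says that it sets out protocol Section 8 in concrete terms, and that section contains the TEAE restriction. New events plus carried-over events is roughly what protocol 7.7.7.11 describes. That is fair as to intent, and a reader should not infer that the sponsor deliberately replaced the definition. But the onset condition on carried-over events is missing from the text, and intent does not supply the filter.

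A reader might also infer that weeks of screening events in new subjects enter the tables, because their events are collected from consent. The documents do not support this. Protocol 8.10 and 8.11.2 point to Visit 2. SAP 10.1 item 8 uses the same phrase and assigns each event a dose at onset, with no zero-dose category, which points to the start of dosing. Item 8 is not decisive, because events in the drug-free follow-up week have no dose at onset either, but nothing favours consent.

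A third tempting inference is that item 1 and item 5 fail to reconcile because of the wider scope. They would differ under the protocol's definition too: valid carried-over TEAEs also have an onset day of 0 or less, and item 5 is confined to the treatment period.

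Three points on size stand against the concern:

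- The carried-over route is narrow. The event must predate the first dose of the preceding study and still be ongoing after its 7-week treatment. Under protocol 7.7.7.1 a symptom recorded as medical history is an adverse event only if it worsens. The preceding study's own collection rules are not in the documents.
- The adverse drug reaction tables should barely change, since protocol 7.7.7.4 classes an event with no valid chronological relationship as not related.
- The protocol's definition does not ensure that every counted event followed duloxetine. The preceding study was placebo-controlled, and protocol 7.7.7.11 makes no exception for events that began on placebo.

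**Conclusion.** The conflict is real and bears on the primary objective. SAP 10.1 admits carried-over events that protocol 7.7.7.11 excludes, and the available text gives no reason. For new subjects the undefined starting point adds registration-day onsets at most, and nothing if first dose was meant.

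The effect is at most 0.74 percentage points per affected subject per table line, assuming an analysis set of 135. The number affected cannot be derived from the documents and is probably small. The case for correction rests on the mismatch between the two documents and on how easily it is removed, rather than on a demonstrated large bias. It should be corrected before the adverse event tables are produced.

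**What to change.** 1. Replace the first sentence of SAP 10.1 with the protocol 7.7.7.11 definition: onset after the first dose in this study or, for consecutive subjects, ongoing at that dose and begun after the first dose in the preceding study.
2. Use the term TEAE in the section 10.1 tables, so that the scope is the same throughout.
3. List adverse events that are not TEAEs separately, so that pre-drug events stay visible without entering the incidences.
4. State in item 5 that carried-over TEAEs, whose onset day is 0 or less, are either left out of the onset-timing categories or shown on their own line. The new definition alone does not settle this.
5. If the wider scope was intended, keep it but give the reason in the SAP, as protocol 8.1 requires.

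The cost is a few lines of SAP text and one filter in the adverse event dataset. Protocol 7.7.7.1 already has the date and time of onset recorded in the CRF. For carried-over events the filter also needs the first-dose date from the preceding study. No new data collection is needed in this study.

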5.2 Dosage and regimen

All subjects will receive oral duloxetine once daily after breakfast for 51 or 52 weeks (a 50-week treatment period and 1- to 2-week tapering period) from the day after registration (Visit 2). Note that, once or twice between Visits 5 and 17, the subjects should visit the study site without taking a dose to collect a blood sample for pre-dose PK (refer to Section 7.6). Table 5-1 shows the treatment regimens for the study drug. During the treatment period, the subjects will receive duloxetine 20 mg/day for one week then 40 mg/day for one week, and subsequently receive either 40 mg/day or 60 mg/day for 48 weeks as appropriate.

Subjects who complete the treatment period or who withdraw from it during Week 2 or later of treatment period will be transferred to the tapering period. During the tapering period, subjects whose duloxetine dose at discontinuation or completion of the treatment period is 60 mg/day will receive 40 mg/day for one week then 20 mg/day for one week. Subjects whose duloxetine dose at discontinuation or completion of the treatment period is 40 mg/day will receive 20 mg/day for one week. However, tapered administration may be omitted if serious adverse drug reactions occur, there are safety-related problems, or the subject or his/her legal representative refuses the tapered administration.

Table 5-1. Treatment Regimens

Treatment period			Tapering period	
Week 1	Week 2	Weeks 3 - 50	Week 51	Week 52
20 mg/day	40 mg/day	60 mg/day	40 mg/day	20 mg/day
1 x 20 mg LY248686 capsule	2 x 20 mg LY248686 capsule	3 x 20 mg LY248686 capsule	2 x 20 mg LY248686 capsule	1 x 20 mg LY248686 capsule
		40 mg/day	20 mg/day	-
		2 x 20 mg LY248686 capsule	1 x 20 mg LY248686 capsule	-

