8.2 Target number of subjects

The target number of subjects is set as at least 100 subjects to collect data from, who receive duloxetine for one year. Assuming that 25% of subjects dropout from this study, the target total number of registered subjects is 135, including consecutive subjects and new subjects. Blood samples for plasma drug concentration measurements will be collected five times for each subject to evaluate the pharmacokinetics in Japanese children and adolescent patients with depressive disorder.

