3.1 Primary objective

To evaluate the long-term safety of duloxetine in children and adolescent patients with depressive disorder.

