4.3 Target number of subjects

135 subjects (targeting 100 subjects complete one year-administration)

Rationale for the target sample size:

In this study, the target number of subjects is set as at least 100 subjects to collect data from, who will receive duloxetine for one year. Assuming that 25% of subjects drop out of this study, the target total number of registered subjects is 135, including consecutive subjects and new subjects.

5. Analysis sets

The efficacy analysis set is defined as the full-analysis set (FAS). In addition, the safety-analysis set will be defined for the analysis of safety.

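### The crude adverse event proportion in SAP 10.1 item 1 is not a one-year risk, and the plan provides no exposure-adjusted or cumulative estimate beside it

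*SAP*

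**What the plan says.** The primary objective is stated as "To evaluate the long-term safety of duloxetine in children and adolescent patients with depressive disorder" (SAP 3.1), in a single open-label arm.

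- **Headline measure.** SAP 10.1 item 1: "The incidence rate will be obtained as the proportion of subjects in the analysis set with a specific adverse event", with a Clopper-Pearson interval. The same calculation serves deaths, other serious events, events leading to discontinuation or dose reduction, and adverse drug reactions. Protocol 8.11.1 agrees: "The TEAE rate and 95% confidence interval will be calculated by the Clopper-Pearson method".
- **Denominator.** The safety-analysis set (SAP 5.2) is every subject dosed at least once, whatever the exposure.
- **Follow-up.** For withdrawn subjects, "the principal investigator or sub-investigator will assess adverse events up to 7 days after final administration of the study drug" (Protocol 7.7.7.2).
- **Dropout and size.** "Assuming that 25% of subjects drop out of this study", "the target total number of registered subjects is 135, including consecutive subjects and new subjects" (SAP 4.3). Protocol 8.2 adds: "The target number of subjects is set as at least 100 subjects to collect data from, who receive duloxetine for one year".
- **Carried-over events.** SAP 10.1 also evaluates events continuing from the preceding study. Protocol 7.7.7.11 makes them treatment-emergent here if they began after dosing started in that study.
- **Exposure-aware output.** SAP 10.1 item 5 tabulates events by onset window, and each denominator is limited to subjects whose dosing lasted at least to the start of the window. SAP 8.1.1 summarises duration of administration.

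Neither document plans a person-time rate, a Kaplan-Meier estimate or a cumulative incidence with an interval.

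**The concern.** A subject observed for three weeks and one observed for the full course weigh the same in item 1, and the quantity called a rate has no time unit. With a quarter of subjects expected to leave, the proportion refers to a mixture of follow-up lengths. The study exists to describe safety over about a year, and what it adds to the 7-week preceding study is mainly information on later events. Those are the events that subjects who leave early cannot contribute. If the item 1 figure is the only overall summary, a label or publication reader has nothing that refers to a stated period of exposure.

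**Working it through.** **Plan's own figure.** 100 / (1 − 0.25) = 133.3, rounded up to 134. The plan states 135, and 135 × 0.75 = 101.25 expected completers. The sample size reproduces to within rounding, so 25% is taken as the dropout d.

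**Model (assumptions; the documents give no event rates, onset pattern or dropout timing).** Scale the planned 50 weeks to 1. Let F be the true risk of a new-onset event over that period, with constant hazard λ = −ln(1 − F). Let dropout be independent of the event, with hazard μ = −ln(0.75) = 0.2877. The taper and the 7-day follow-up are ignored.

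Mean exposure = (1 − 0.75)/0.2877 = 0.869 of the planned period.

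Expected crude proportion = λ/(λ + μ) × [1 − (1 − F)(0.75)].

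- F = 10%: 0.1054/0.3930 × (1 − 0.675) = 8.7%
- F = 20%: 0.2231/0.5108 × (1 − 0.600) = 17.5%

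| True risk | Expected crude | Relative shortfall |
|---|---|---|
| 5% | 4.35% | 13.0% |
| 10% | 8.7% | 12.9% |
| 20% | 17.5% | 12.6% |
| 30% | 26.3% | 12.4% |
| 50% | 44.2% | 11.7% |

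At a true 10%, that is 11.8 subjects of 135 instead of 13.5. With dropout of 15% or 35% instead of 25%, the shortfall at a true 10% is about 8% or 18%.

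**Onset timing.** If onsets are spread evenly between scaled times a and b, the share observed is (0.75^a − 0.75^b)/[(b − a)μ].

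- Weeks 0 to 8: 0.977, a shortfall of about 2%
- Weeks 24 to 50: 0.809, about 19%
- Weeks 40 to 50: 0.772, about 23%

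**Dropout timing.** If all dropouts leave at week 8 and F = 10%: 0.75 × 0.10 + 0.25 × (1 − 0.9^(8/50)) = 7.9%, or 21% low. At week 2 it is 24% low. The limit is 0.75F, a 25% shortfall, when dropouts contribute no events.

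**Does item 5 recover the risk?** Chaining its windows to week 50, using first events only:

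| True risk | Crude | Item 5 denominators | Prior cases removed from risk set |
|---|---|---|---|
| 10% | 8.7% | 9.4% | 9.8% |
| 30% | 26.3% | 26.0% | 29.4% |

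Item 5 as written keeps prior cases in the denominator. It helps for uncommon events but not for common ones, and the SAP does not ask for the chaining.

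**Carried-over events.** If a share c of the safety set enters with the event, the crude figure at a true 10% becomes c + (1 − c) × 0.0871. Setting this to 0.10 gives c = 0.0129/0.9129 = 1.4%, which cancels the shortfall. With c = 5% the figure is 13.3%.

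**Scale of sampling error.** 12/135 = 8.9% has a Clopper-Pearson interval of 4.7% to 15.0%. The 1.3-point shortfall at a true 10% is well inside it, but it is systematic.

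**The case against.** The case for leaving the plan alone has real force.

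- **The target is a choice.** Neither document calls the item 1 figure a one-year risk. The 100 one-year subjects are a data-collection target resting on ICH E1 (Protocol 3.2). With a fixed planned course there is essentially no administrative censoring, so the crude proportion is the incidence of events observed under actual exposure, with withdrawal as a competing event, and Clopper-Pearson is a proper interval for it. This stands: item 1 is not wrong for what it measures.
- **Outright understatement.** A reader might infer that the analysis simply understates risk. The documents do not support that. Carried-over events act the other way, early-onset events lose almost nothing, and Protocol 4.5 lists serious or intolerable adverse events and worsening disease as reasons to stop, so dropout may well be informative.
- **Worst for serious, suicide-related and discontinuation events.** A reader might also infer this. It is not shown: an event that causes discontinuation is itself counted, and independence of dropout cannot be assumed for the others.
- **Existing output.** Item 5 does adjust for early discontinuation, and SAP 10.5 summarises C-SSRS at each time-point, so suicidality does not rest on item 1 alone. But item 5 gives no cumulative figure and no interval, and it is by system organ class and preferred term, not for the serious, discontinuation or SMQ groupings. The SMQ table in item 7 has neither an interval nor an exposure adjustment.
- **Size.** The bias is smaller than the sampling error at this sample size, and a single arm has no between-arm imbalance in exposure. That limits the urgency, not the point.

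**Conclusion.** The point holds in a limited form. Item 1 is a sound description of events seen during actual exposure, but it cannot be read as a risk over the planned year, and nothing else in the plan supplies that risk with an interval. For new-onset events, with 25% dropout, constant hazards and dropout unrelated to the event, the relative gap is about 13%, ranging from about 2% for onset in weeks 0 to 8 to about 19% to 23% for late onset, with a ceiling of 25% under non-informative dropout. Because carried-over events raise the figure and informative dropout could alter the gap in size or direction, the net bias is not determined by the documents. This is a worthwhile low-cost addition for a study whose primary objective is long-term safety, not the correction of an error in item 1.

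**What to change.** Keep the crude proportion and its Clopper-Pearson interval in SAP 10.1 item 1, described as incidence over actual exposure. For any TEAE, serious TEAEs, TEAEs leading to discontinuation, adverse drug reactions and the two SMQs in item 7, add:

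1. first-event rates per 100 patient-years at risk;
2. cumulative incidence at week 50 with a 95% CI, as one minus Kaplan-Meier with withdrawn subjects censored at the end of their adverse event assessment. Name the estimator: treating withdrawal as a competing event would largely return the crude figure.

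Restrict both to events with onset on or after the first dose in this study, tabulate carried-over events separately, and state that the Kaplan-Meier estimate assumes non-informative censoring, which is doubtful where withdrawal is linked to worsening or tolerability.

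The cost is a little programming. Onset dates (Protocol 7.7.7.1) and dosing duration (Protocol 5.9) are already recorded, so no new data are needed. Some reported risks will become slightly less favourable.

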7.7 Safety evaluation

7.7.1 Physical examination

At Visits 1 (or Visit 2 for consecutive subjects) to 18 (or discontinuation of the treatment or tapering period) and Visit 19, the principal investigator or sub-investigator will examine the subject by the standard methods in use at the relevant institution, and will ascertain the occurrence or non-occurrence of adverse events.

When an adverse event is found, the details will be recorded in the CRF. If necessary, examination appropriate to the signs and symptoms will also be performed, as judged appropriate by a physician. For 2 weeks after the initial administration of the study drug, the subject's progression will be monitored with special care.

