- 6) With subjects in the safety analysis set who are transferred to the tapering period, adverse events that occur during the tapering period will be summarized. The number of subjects with a given adverse event, the number of cases, and the incidence rate will be determined by adverse event system organ class and preferred term. However, when calculating the number of subjects with a given adverse event and the incidence rate, if the same adverse event occurs more than once with the same subject, these events will be taken to be have affected one subject. Adverse drug reactions will be tabulated similarly.
- 7) With respect to adverse events for which the following standard MedDRA queries (SMQ) are applicable, the number of subjects, number of cases, and incidence rate will be determined by system organ class and preferred term. However, when calculating the number of subjects with a given adverse event and the incidence rate, if the same adverse event occurs more than once with the same subject, these events will be taken to be have affected one subject.

SMQ	Range
Suicide/self-injury	Broad search
Hostility/aggression	Broad search

- 8) The number of subjects and incidence rate will be calculated for each study drug dose category (20 mg, 40 mg, 60 mg, 540 mg) at the onset date of adverse event occurring after the initiation of the open-label extension study, by system organ class and preferred term. When calculating the number of subjects and the incidence rate, if the same adverse event occurs in different categories

more than once in the same subject, it will be taken to have occurred with one subject in each of the relevant categories. Adverse drug reactions will be tabulated similarly.

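### No adverse-event table in the SAP isolates the first 2 weeks of treatment, which the protocol singles out for special care

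*SAP*

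**What the plan says.** Protocol 7.7.1 attaches its call for special care to a defined window: "For 2 weeks after the initial administration of the study drug". Protocol 5.2 fixes the dose in the same window: "the subjects will receive duloxetine 20 mg/day for one week then 40 mg/day for one week". From week 3 the dose is 40 or 60 mg/day. Protocol 3.1 tapers subjects on 60 mg through a week at 40 mg and a week at 20 mg, and subjects on 40 mg through a week at 20 mg.

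Protocol 8.11.1 requires treatment-emergent adverse events to be summarised by onset timing and leaves the categories open. SAP 10.1 then specifies:

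- Item 5, by onset: "weeks 0 to 8; weeks 8 to 16", continuing in 8-week bands to week 48, then weeks 48-50 and later than week 50. The denominator is the "number of subjects with administration duration no shorter than the lower limit of each onset time category".
- Item 6, taper: "adverse events that occur during the tapering period will be summarized", by system organ class and preferred term, without a dose split.
- Item 8, by dose: "each study drug dose category (20 mg, 40 mg, 60 mg, 540 mg) at the onset date of adverse event", without a split by study phase.
- Items 1-4 and 7 (overall counts, system organ class and preferred term, events at 2% or more, severity and outcome, and the two MedDRA queries) have no time split.

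**The concern.** The primary objective is long-term safety, and suicide-related adverse events are named as of special concern (Protocol 7.7.7.6.1). Events that cluster at treatment start or at the first dose step would enter the weeks 0-8 row together with six later weeks. A reader of the onset table could not tell a start-up cluster from an even spread over 8 weeks. The end of treatment is handled more finely: item 5 has a 2-week row for weeks 48-50, and item 6 gives the taper its own table. The start of treatment has no equivalent.

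**Working it through.** **1. The plan's own figure.** The only design figure is the sample size: 100 / (1 - 0.25) = 133.3, so 134, against 135 stated; 135 × 0.75 = 101.25. It reproduces. It matters here only as the largest possible denominator for a first-weeks row.

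**2. Share of the first onset row.** Days 1-14 out of 56: 14/56 = 25%.

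**3. Can the by-dose table recover those days?** Nominal days per dose row for a subject who completes treatment and taper (Protocol 3.1 and 5.2; maintenance is 48 × 7 = 336 days):

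| Row | Maintenance dose | Titration | Maintenance | Taper | Titration share |
|---|---|---|---|---|---|
| 20 mg | 40 or 60 mg | 7 | 0 | 7 | 7/14 = 50% |
| 40 mg | 40 mg | 7 | 336 | 0 | 7/343 = 2.0% |
| 40 mg | 60 mg throughout | 7 | 0 | 7 | 7/14 = 50% |

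If a fraction f of subjects is on 60 mg throughout weeks 3-50 (assumed; the documents give no figure), the titration share of the pooled 40 mg row is 7 / [7 + 7f + 336(1 - f)]. This is 2.7% for f = 0.25, 3.9% for f = 0.50 and 7.3% for f = 0.75.

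Subtracting the taper table does not help. It is not split by dose, each subject is counted once per event within a table, and week 2 would stay merged with 40 mg maintenance.

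**4. What pooling can hide.** Suppose 20 of 135 subjects each have one event in weeks 0-8 and all stay on treatment. The entry is 20/135 = 14.8% in both cases below.

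- 5 fall in weeks 0-2: 5/(135 × 2) = 1.85 per 100 patient-weeks, then 15/(135 × 6) = 1.85.
- All 20 fall in weeks 0-2: 20/(135 × 2) = 7.4 per 100 patient-weeks, then 0.

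**5. Attenuation of an early excess.** Assume a background risk of 1% per week, multiplied by k in weeks 0-2. The pooled risk is 1 - (1 - 0.01k)² × 0.99⁶, and weeks 8-16 give 1 - 0.99⁸ = 7.7%.

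| k | Weeks 0-8 | Ratio to weeks 8-16 |
|---|---|---|
| 2 | 1 - 0.98² × 0.99⁶ = 9.6% | 1.2 |
| 3 | 1 - 0.97² × 0.99⁶ = 11.4% | 1.5 |
| 5 | 1 - 0.95² × 0.99⁶ = 15.0% | 1.9 |

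For low weekly risks the ratio tends to (2k + 6)/8, that is 1.25, 1.5 and 2.0. The 1% is therefore not critical.

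**6. Why the split rows need a per-week reading.** For k = 3, weeks 0-2 give 1 - 0.97² = 5.9% and weeks 2-8 give 1 - 0.99⁶ = 5.9%, which look equal. Per week they are 5.9/2 = 2.95% and 5.9/6 = 0.98%, and the 3-fold difference is visible again.

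**7. Precision of a weeks 0-2 row.** Exact (Clopper-Pearson) 95% limits at n = 135: 0 subjects, 0-2.7%; 5 subjects, 1.2-8.4%; 10 subjects, 3.6-13.2%.

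**The case against.** The strongest reply is that nothing in the documents is breached. Protocol 7.7.1 is an instruction on monitoring and does not ask for a table. Protocol 8.11.1 leaves the categories open, and equal 8-week bands suit a long-term safety objective. That stands: a reader might infer that the SAP contradicts the protocol, and it does not.

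A reader might also infer that early suicidality goes unreported. It does not: SAP 10.5 item 2 summarises C-SSRS at every scheduled treatment visit, and SAP 9.1.1 summarises CDRS-R item 13 at each time-point, so both appear at weeks 1 and 2. Suicide-related adverse events also go to the sponsor and on to committee review (Protocol 7.7.7.6.1). The incidence of suicide-related adverse events in those weeks, however, appears in no specified table.

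Two other readings go too far. Weeks 0-8 do not hold every dose step, since 40/60 mg changes may occur until week 50 (Protocol 3.1); a finer first row does not address those. And the 20 mg row contains no maintenance by schedule; it mixes week 1 with taper only.

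Finally, a pooled weeks 0-2 row would itself blend first exposure with re-titration in consecutive subjects who had duloxetine in the preceding study. That is correct, and the fix allows for it. The mock tables are a separate document and might contain more; the SAP text does not commit to it.

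**Conclusion.** The point holds as a minor reporting gap in the adverse-event and adverse-drug-reaction tables. The special-care fortnight is a quarter of the first onset row, and no other adverse-event table specified in the SAP recovers it. An early excess would be attenuated, not lost: 2-, 3- and 5-fold weekly excesses appear as about 1.2-, 1.5- and 1.9-fold. Those ratios rest on an assumed constant background of 1% per week and an excess confined to weeks 0-2. The day shares rest on the nominal schedule, without visit-window shifts or early withdrawal.

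**What to change.** In SAP 10.1 item 5, replace the first category with weeks 0-2, 2-4 and 4-8, which end at Visits 4, 5 and 6. Apply the existing denominator rule to each row, and keep weeks 0-8 as a subtotal so that it stays comparable with the later 8-week bands. A subject may count once in each row, so the subtotal need not equal their sum. Because the rows differ in width, report or read them per week of exposure.

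Show the weeks 0-2 row separately for new subjects and for consecutive subjects by preceding-study treatment group, a grouping that SAP 7.2 already uses. For those previously on duloxetine these weeks are re-titration.

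Onset dates are already recorded (Protocol 7.7.7.1), so no new data are needed, and since the protocol does not fix the categories it needs no amendment. The cost is one edited SAP list, a slightly longer table and small counts in the new rows, smaller still within subgroups.
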